12.2 Assessment of Causal Relationship

The investigator must assess the relationship of any AE to the use of study drug, based on available information, using the following guidelines:

- **Unrelated:** There is not a reasonable possibility that the drug caused the event.
- **Related:** There is a reasonable possibility that the drug caused the event; “reasonable possibility” means there is evidence to suggest a causal relationship between the study drug and the AE.

12.3 Action Taken

For each reported AE, the investigator must document the action taken according to the following criteria:

- No action taken
- Non-pharmacologic treatment
- Pharmacologic treatment
- Discontinued from study drug
- Discontinued from study
- New or prolonged hospitalization

12.4 Adverse Event Outcome

For each reported AE, the investigator must document the outcome according to the following criteria:

- Recovered
- Ongoing
- Unknown
- Death

12.5 Expedited Safety Reports to Health Authorities

Sponsor or designate will be responsible for reporting expedited and periodic safety reports to health authorities in accordance with the requirements of individual countries.

For SAEs that require expedited regulatory reporting in the U.S. under 21 Code of Federal Regulations (CFR) 312.32(c)(1), the sponsor will notify the FDA and all participating investigators in a written IND safety report.

13 DATA MANAGEMENT

Study data will be entered into eCRFs at the study sites (Section 15.7). Prior to database lock, programmed computer edit checks will be run against the database to check for discrepancies and reasonableness of the data. All issues resulting from the computer-generated checks as well as manual data review will be resolved prior to database lock.

14 STATISTICAL ASSUMPTIONS

14.1 Statistical Methods and Planned Analyses

14.1.1 Endpoints

The primary endpoints for safety will be:

- The proportion of subjects with TEAEs
- The proportion of subjects with therapy not tolerated. Therapy not tolerated will be defined as discontinuation of drug treatment due to a related AE.

Secondary endpoints include efficacy of solithromycin or active comparator as evidenced by clinical response (see Section 10.7) and population PK of solithromycin.

14.1.2 Sample Size

Subjects will be randomized 3:1 (solithromycin 300: comparator 100), stratified by age, with at least 40 subjects randomized per age group. The sample size of 300 in the solithromycin group is based on the ability to observe an SAE at a frequency higher than 1% (Table 11).

Table 11 Probability of Observing at Least one Subject with a Serious Adverse Event

Number of Subjects	Possible Serious Adverse Event Incidence with 5 Days of Dosing				
	0.1%	0.25%	0.5%	1%	2%
100	0.095	0.22	0.39	0.63	0.87
200	0.18	0.39	0.63	0.87	0.98
300	0.26	0.53	0.78	0.95	>0.99

In addition, this sample size will provide reasonable estimates and 95% CI for safety. If 1 subject has an AE, then the 95% CI (exact binomial) for that AE within the subject population of 300 subjects is 0, 1.8% (see Table 12).

Table 12 Proportion of Subjects with Adverse Events and 95% CI

Number of Events	Proportion	95% CI
0	0	0, 0.012
1	0.003	0.0001, 0.018
2	0.007	0.001, 0.024
3	0.010	0.002, 0.029

14.1.3 Safety Analysis

For the primary safety endpoints, the frequency and percentage of subjects with AEs and therapy not tolerated will be determined and 95% CIs calculated. Summaries will be calculated by treatment group for the overall safety population and stratified by age group.

Additional safety analyses include summaries of AEs, descriptive statistics of laboratory values, descriptive statistics of vital signs, and frequency distributions of abnormal physical examinations. Laboratory data, such as hematology and serum chemistry data, as well as safety data will be analyzed. Summary statistics for changes from baseline and shift tables will be presented. Continuous laboratory measurements will be described at each visit using descriptive statistics (mean, median, etc.); observed values and changes from baseline will be summarized. Laboratory tests reflective of liver toxicity (e.g., ALT, AST) will be further summarized in terms of the most extreme values and largest changes from baseline (in the appropriate direction) observed from start of study drug through the end of therapy. All analyses will include summaries for both treatment and active comparator.

Additional details of safety analyses will be included in the Statistical Analysis Plan (SAP).

14.1.4 Pharmacokinetic Analysis

A population PK analysis will be performed using non-linear mixed effects modeling in NONMEM. Data will be reviewed during the study to evaluate the PK of solithromycin in pediatric CABP patients. The influence of covariates on PK parameters will be explored. Monte Carlo simulations will be used to evaluate optimal drug exposure. The relationship between drug exposure and safety events will be evaluated by calculating the proportion of subjects with AEs and SAEs at different exposure levels.

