Any study team member may perform safety assessments. An independent Data Monitoring Committee will assess the overall study status and safety of subjects at intervals outlined in the committee's charter and will make recommendations to the sponsor on continuing or modifying the study based on these assessments.

Efficacy:

A health care provider designated as a subinvestigator blinded to treatment allocation at the site will document clinical response at specified time points during the study.

Pharmacokinetics:

The table below provides the optimal plasma sampling collection windows for solithromycin according to route of administration. Every effort should be made to collect at least 2 PK samples on Day 1 and at least 2 PK samples on days 3 through 7 during these windows (not to exceed 6 samples total); however, samples obtained outside of the sampling windows are acceptable. Lack of collection of samples or collection outside the optimal windows will not be considered protocol deviations.

IV Time after dose	Oral Time after dose
Prior to dosing (within 1 hour) ^a	Prior to dosing (within 1 hour) ^a
End of infusion (within 10 minutes)	0.5–1.5 hours
2–4 hours	2–4 hours
8–10 hours	8–10 hours
16–18 hours	16–18 hours
20–<24 hours	20–<24 hours

^a Not applicable to Day 1 samples.

Statistical Methods and Data Analysis

Efficacy population: All subjects who are randomized.

Safety population: All subjects who receive at least 1 dose of study drug.

PK population: All subjects who receive at least 1 dose of solithromycin and have at least 1 evaluable PK sample.

MicroITT population: Randomized subjects who have a microbiologically confirmed baseline pathogen.

Safety:

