New events that occur or pre-existing conditions that worsen in frequency or intensity will be reported as AEs or SAEs. AEs will be reported for 16 days and SAEs for 28 days post-randomization. The investigator will provide date of onset and resolution, intensity, frequency, actions taken, changes in study drug dosing, relationship to study drug, and outcome. Laboratory determinations performed by local laboratories including hematology values (hemoglobin, hematocrit, WBC count with differential, and platelet count) and serum chemistry values (blood urea nitrogen, calcium, serum creatinine, potassium, sodium, AST, ALT, alkaline phosphatase, total and direct bilirubin, and albumin) obtained within 72 hours prior to the first dose of study drug and while the subject is on therapy will be recorded. Baseline and on-study microbiological cultures of blood, cerebrospinal fluid (CSF), pleural fluid, and respiratory secretions will be recorded if obtained within 72 hours prior to the first dose of study drug and while the subject is on therapy. If an AE or SAE occurs, concomitant medications will be recorded at the time of the event.

Primary safety endpoints will be the proportion of subjects experiencing an AE and the proportion of subjects discontinuing study drug due to a related AE. Additional safety analyses include summaries of AEs, descriptive statistics of laboratory values, frequency distributions and shift tables summarizing abnormal laboratory values, descriptive statistics of vital signs, and frequency distributions of abnormal physical examinations.

Efficacy:

The primary efficacy endpoint is defined as clinical improvement on the last day of treatment (end of treatment response), and the secondary efficacy endpoints are defined as early clinical response at Days 2-4 and clinical success (i.e., cure) at the short-term follow-up visit (16 days [+/- 4 days] post-randomization).

Pharmacokinetics:

Population PK methodologies using nonlinear mixed effects modeling in NONMEM will be used to analyze the concentration data. Data will be reviewed during the study to evaluate PK of solithromycin in pediatric CABP patients. The influence of covariates on PK parameters will be explored. Monte Carlo simulations will be used to evaluate optimal drug exposure. The relationship between drug exposure and safety events will be evaluated by calculating the proportion of subjects with AEs and SAEs at different exposure levels.

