10.4.3 Pharmacokinetic Determinations

Solithromycin concentrations will be measured in plasma. Pharmacokinetics samples will be processed at a central lab using a validated bioanalytical assay. These data will be reviewed periodically during the study. Two PK samples (150 μ L per sample) will be collected on Day 1. Additional PK samples (150 μ L per sample) will be collected at varying time points on Days 3 to 7 (maximum of 6 PK samples taken total). Every effort should be made to collect at least 2 PK samples on Day 1 and additional PK samples on Days 3 to 7. Table 10 below provides the optimal sampling collection windows for solithromycin according to route of administration. Every effort should be made to collect PK samples during the time windows provided; however, samples obtained outside of the sampling windows are acceptable. Lack of collection of samples or collection outside the optimal windows will not be considered protocol deviations. No more than 6 PK samples will be collected per subject. For subjects switched from an IV to oral formulation, the oral sampling scheme can be used following all subsequent oral doses.

Table 10 Optimal Pharmacokinetics Sampling Windows Following Dose Administration

Intravenous Time after dose	Oral Time after dose
Prior to dosing (within 1 hour) ^a	Prior to dosing (within 1 hour) ^a
End of infusion (within 10 minutes)	0.5–1.5 hours
2–4 hours	2–4 hours
8–10 hours	8–10 hours
16–18 hours	16–18 hours
20–<24 hours	20–<24 hours

a. Only applicable to Days 3 to 7 PK samples.

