2 PURPOSE OF THE ANALYSIS PLAN

The purpose of this statistical analysis plan (SAP) is to give a brief overview of the study design and study objectives for Cempra, Inc. study CE01-203, outline the types of analyses and presentations of data relevant to the study objectives, and to provide a detailed description of the method in which the statistical analyses will be conducted to meet protocol objectives.

The scope of this plan applies primarily to the evaluation of the safety and efficacy objectives of the study as presented in the clinical protocol. The analyses of pharmacokinetic (PK) data will be conducted according to the PK data analysis plan contained as an appendix to this document. The SAP is based on the study protocol (Protocol CE01-203) and the electronic Case Report Form (eCRF) that were in effect at the date this SAP was finalized. An update to this SAP may be necessary if the protocol and/or eCRF are updated in a manner that affect the planned analyses. The Duke Clinical Research Institute (DCRI) on behalf of the sponsor (Cempra, Inc.) will conduct all statistical analyses detailed in this SAP.

It is intended that all statistical analyses specified in the protocol will be performed. However, it is conceivable that due to the manner in which the study unfolds, some scheduled analyses may not be performed. In addition, study conditions or analysis results may suggest the need for additional statistical analyses of the collected study data. In either case, deviations from the planned statistical analysis will be fully described in the final clinical study report. Furthermore, any additional analyses performed beyond those specified in the protocol or this SAP will be descriptive in nature and will not include hypothesis testing for the purposes of inferential conclusions.

In March 2018, the CE01-203 trial was terminated, because the sponsor discontinued development of Solithromycin. As a result of the early termination, the final number of enrolled participants was fewer than one quarter of the originally-planned sample size of 400. In consultation with the study investigators and the sponsor, the planned statistical analyses laid out in this SAP were curtailed due to the limited sample size particularly within age subgroups.

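### The stated exposure-safety method groups a continuous exposure into levels; a logistic model on log AUC0-24 would use more of the data and give a slope with an interval

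*Protocol*

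**What the plan says.** Protocol 14.1.4 (Pharmacokinetic Analysis) opens: "A population PK analysis will be performed using non-linear mixed effects modeling in NONMEM". The same paragraph then gives the exposure-safety method: "The relationship between drug exposure and safety events will be evaluated by calculating the proportion of subjects with AEs and SAEs at different exposure levels". The Synopsis, under Pharmacokinetics, repeats it: "by calculating the proportion of subjects with AEs and SAEs at different exposure levels". Neither place names the exposure metric, the number of levels, the cut-points, an effect measure, a model or a test.

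The SAP's main text and its list of tables, figures and listings (Section 12) contain no exposure-safety output. SAP Section 2 refers the matter elsewhere: "The analyses of pharmacokinetic (PK) data will be conducted according to the PK data analysis plan contained as an appendix to this document". That appendix was not part of the text available for this review.

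Individual exposures exist only for the PK population, which the Synopsis defines as "All subjects who receive at least 1 dose of solithromycin and have at least 1 evaluable PK sample". Protocol 10.4.3 tolerates missing samples: "Lack of collection of samples or collection outside the optimal windows will not be considered protocol deviations".

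**The concern.** A population PK model yields an individual AUC0-24 or Cmax on a continuous scale. Cutting that scale into levels treats all children within a level as alike. Exposure is widely spread here. Adolescent Day 3-5 AUC0-24 had mean 9.28 and SD 6.30 (Protocol Table 3), and for the IV dose the simulated SD exceeds the median in every age group, for example 14.4 (23.4) at 12-17 years (Protocol 5.4). Unstated cut-points can also be chosen after the data are seen, whereas a slope needs none.

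The question matters in this programme. Paediatric doses were chosen to match adult exposure (Protocol 5.4), and Protocol 5.2.4.1 reports an exposure-response relationship for ALT elevation in adults. A set of raw proportions shows neither how steep a gradient is nor how steep a gradient the data could exclude.

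**Working it through.** **1. The plan's own figure.** No power is stated for the exposure-safety analysis. The 300 rests on observing at least one SAE: at 1% incidence, 1 − 0.99^300 = 0.951, matching the 0.95 in Protocol Table 11. All 15 cells of that table and the Table 12 limits reproduce. None of this bears on detecting a slope.

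**2. Inputs for the comparison.**
- Spread of log AUC, from Protocol Table 3: CV = 6.30/9.28 = 0.679; SD of log AUC = √ln(1 + 0.679²) = 0.616.
- Assumed: log-normal AUC known without error; two-sided 5% level; AE rate 36%; odds ratio 1.5 per doubling of AUC. Per SD of log AUC the slope is (ln 1.5 / ln 2) × 0.616 = 0.360, an odds ratio of e^0.360 = 1.43 per SD.
- N = 300 is the planned solithromycin arm. N = 75 is the ceiling implied by fewer than a quarter of 400 enrolled (SAP Section 2) at 3:1: 100 × 3/4 = 75.

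**3. Hand approximation at N = 300.** The expected z is √(300 × 0.36 × 0.64) × 0.360 = 8.31 × 0.360 = 2.99, so power is Φ(2.99 − 1.96) = Φ(1.03) ≈ 0.85. A median split of a normal variable keeps a fraction 2/π of the information, so z falls to 2.99 × √(2/π) = 2.39 and power to Φ(0.43) ≈ 0.67.

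**4. Simulation of the same scenario (4000 trials).**

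| Analysis | Power, N = 300 | Loss (points) | Power, N = 75 | Loss (points) |
|---|---|---|---|---|
| Continuous log AUC | 0.835 | – | 0.301 | – |
| Median split | 0.652 | 18 | 0.211 | 9 |
| Tertiles, unordered chi-square | 0.648 | 19 | 0.181 | 12 |
| Quartiles, unordered chi-square | 0.626 | 21 | 0.166 | 14 |
| Tertiles, ordered trend | 0.741 | 9 | 0.26-0.27 | 3-4 |
| Quartiles, ordered trend | 0.774 | 6 | 0.26-0.27 | 3-4 |

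The simulation agrees with step 3.

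**5. Range.** At N = 300, over AE rates of 20-50% and odds ratios of 1.3-1.7 per doubling, the loss is about 8-24 points against a median split or unordered comparison and about 2-10 points against an ordered trend.

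**6. Rarer events at N = 300** (odds ratio 1.3-1.5 per SD). At a 7% rate, close to the adult 7.2% with ALT above 3×ULN, continuous power is 0.21-0.42. The loss is 6-15 points (median split), 2-8 (trend) or 8-19 (unordered). At 2%, continuous power is 0.10-0.16 and any grouping loses 1-8 points.

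**7. Missing PK samples.** If only 225 of 300 children had a usable exposure (an assumed figure), then at a 35% rate and odds ratio 1.4 per SD the continuous model has power 0.65. The loss is 17-22 points against a median split or unordered test and 6-9 against a trend. Power falls for all methods, but the gap remains.

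**The case against.** The method document is out of view. Protocol 14.1.4 is a one-sentence summary and the PK analysis plan may already contain a model. A reader might infer that grouped proportions are the only exposure-safety analysis; the documents available do not establish that. They show only that this is the method the protocol states.

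The plan specifies no test here, and its safety and efficacy analyses are descriptive throughout. A power loss therefore has to be measured against a test supplied by the reader, and the median split and unordered chi-square are the unfavourable choices. This stands: no single loss figure belongs to the plan, and an ordered trend recovers much of the gap.

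A reader might also suppose that every treated child has an exposure. The PK population definition and the tolerance of missed samples say otherwise. With at most six sparse samples, each AUC is itself estimated with error, so the absolute powers above are optimistic. The CV comes from a 13-adolescent capsule study at 12 mg/kg then 6 mg/kg, with Day 3-5 AUC available in 10. This trial spans 2 months to 17 years, three formulations and other doses.

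The liver argument needs care. Protocol 12.1 does not count laboratory abnormalities as AEs unless they are symptomatic or need intervention, though one that leads to stopping or interrupting study drug will usually count. Regressing AEs on exposure would therefore largely miss asymptomatic ALT rises. This is correct, and it is why ALT must be a separate outcome.

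Finally, with about 75 or fewer children several adjusted models would be fragile. That argues for a small, exploratory set of models. It does not argue for grouping, which is no more robust at that size.

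**Conclusion.** The point holds as an inexpensive improvement to a secondary analysis. The protocol's stated method groups an exposure that its own PK model can supply continuously, and gives neither slope nor interval. For common events and moderate slopes at 300 children the cost is about 8-24 points of power against a median split or unordered comparison, and about 2-10 points against an ordered trend. These figures rest on assumed event rates and slopes, error-free exposure, and a CV from one small adolescent study; the documents give no paediatric slope.

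It would be tempting to conclude that the loss is greatest in the small number actually enrolled. The calculation shows the reverse. In the worked scenario it falls to about 9-14 points (median split or unordered) or 3-4 (trend), and the continuous model itself has only about 30% power. At that size the benefit is mainly an odds ratio whose interval shows what the data can and cannot exclude.

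**What to change.** In Protocol 14.1.4, the Synopsis and the PK analysis plan:

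- Make the main exposure-safety analysis a logistic regression in the PK population on log individual AUC0-24, adjusted for age group. Use the SAP's two consolidated age groups if numbers are small.
- Fit it for any TEAE, any SAE, and ALT above a stated multiple of ULN.
- Report the odds ratio per doubling of AUC0-24 with its 95% CI. Use log Cmax as a secondary metric and Firth's penalised likelihood where events are sparse.
- Keep the proportions by exposure level as the descriptive display and as a check on linearity, with the number of levels and the cut-points stated.
- Label the analysis exploratory. If the PK analysis plan already contains such a model, cite it in the protocol text.

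The cost is a few models on data the plan already produces; no visit, sample or dose changes. The drawbacks are an assumed log-linear effect, which the retained display helps to check, and several estimates without multiplicity control.

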In the Phase 3 IV to oral CABP study, 5 (1.2%) patients in the solithromycin group and 7 (1.6%) patients in the moxifloxacin group died during the study. None of the SAEs resulting in death was considered related to study drug. A total of 30 (6.9%) patients in the solithromycin group and 23 (5.4%) patients in the moxifloxacin group reported at least 1 non-fatal SAE. Only 3 SAEs were considered related to study drug by the investigators (urticaria and anaphylactic reaction in 1 patient each in solithromycin and anaphylactic reaction in 1 moxifloxacin patient). The most frequently reported infusion site related TEAEs were infusion site pain (10.4%), infusion site phlebitis (10.0%) and infusion related reaction (6.5%). Infusion site related TEAEs were mostly mild or moderate in intensity and infrequently led to discontinuation of study drug or withdrawal from the study (in 1 moxifloxacin and 10 solithromycin patients). Apart from infusion site related events, the most common AEs observed in patients receiving solithromycin were diarrhea (5.9%) and headache (4.2%).

In the adolescent oral phase 1 study (CE01-119), 12 AEs were reported, of which 9, including 1 SAE (limb abscess), were unrelated to solithromycin. Three subjects had AEs related to study drug: 2 separate episodes of mild headache and 1 episode of increased transaminases ($<3\times$ ULN).

The most common AEs reported after multiple IV doses were general disorders and administrative site conditions (infusion-related pain) followed by nervous system disorders and vascular disorders (phlebitis), with the majority mild in severity.

Solithromycin, like most antibiotics and like all macrolide antibiotics, has been associated with hepatic aminotransferase elevations. In the pooled Phase 3 CABP trials, ALT elevations to $>3\times\text{ULN}$, $>5\times\text{ULN}$ and $>10\times\text{ULN}$ were seen in 7.2%, 2.4% and 0.1% of solithromycin recipients compared to 3.6%, 1.0% and 0.2% of moxifloxacin recipients. Elevations of ALT to $>3\times\text{ULN}$ were 5.4% in the oral study and 9.1% in the IV to oral study. These elevations were typically asymptomatic, not associated with bilirubin elevation and readily reversible, with improvement in many cases seen during continued dosing. There have been no Hy's Law cases.

Multiple lines of evidence point to an exposure-response relationship for ALT elevation with solithromycin.

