12.1 Adverse Events

An AE is any untoward medical occurrence associated with the use of a study drug in humans, whether or not considered drug related. An AE can be a clinical event in the form of signs, symptoms, disease, or laboratory or physiological observations occurring in a human being participating in a clinical study with study drug or comparator, regardless of causal relationship. A “pre-existing” condition is one that is present prior to study drug administration and is reported as part of the subject’s medical history. A pre-existing condition should be reported as an AE only if the frequency, intensity, or character of the pre-existing condition worsens during the course of the study.

Laboratory abnormalities are not considered AEs unless they are associated with clinical signs or symptoms, or require medical intervention. However, a clinically significant laboratory abnormality (e.g. detected on clinical chemistry or hematology) that is independent from the underlying medical condition and that requires medical or surgical intervention, or leads to study drug interruption or discontinuation, will usually be considered an AE.

Lack of efficacy/clinical failure is captured as an efficacy measure and in general will not be considered an AE.

Adverse events will be collected from the time of signing of the informed consent until 28 days post-randomization. In addition, the investigator (or designee) should seek to elicit any clinical or objective reactions by specific questioning (“How have you been feeling?”) and, as appropriate, by examination. Information on all AEs should be recorded on the eCRF. All clearly related signs, symptoms, and results of diagnostic procedures performed because of an AE should be grouped together and recorded as a single diagnosis. The component parts of the diagnosis may be listed for verification. If the AE is a laboratory abnormality that is part of a clinical condition or syndrome, it should be recorded as the syndrome or diagnosis rather than the individual laboratory abnormality.

To avoid vague, ambiguous, or colloquial expressions, all AEs should be recorded in standard medical terminology on the eCRF and on the medical record rather than in the subject’s own words. Each AE will also be described in terms of duration (start and stop date and times), severity, association with the study drug, action(s) taken, and outcome.

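### As written, the exposure-safety analysis counts only AEs and SAEs, so it would probably miss most symptom-free ALT elevations, an effect the protocol itself ties to exposure

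*Protocol*

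**What the plan says.** Protocol Section 14.1.4 gives a single rule: the link between exposure and safety is to be "evaluated by calculating the proportion of subjects with AEs and SAEs at different exposure levels". The synopsis repeats it.

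Section 12.1 decides what counts as an AE: "Laboratory abnormalities are not considered AEs unless they are associated with clinical signs or symptoms, or require medical intervention". It then adds an exception. A clinically significant abnormality that is independent of the underlying condition and requires intervention, or that "leads to study drug interruption or discontinuation, will usually be considered an AE".

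Section 5.2.4.1 says of the adult data: "Multiple lines of evidence point to an exposure-response relationship for ALT elevation with solithromycin". It also says: "These elevations were typically asymptomatic, not associated with bilirubin elevation and readily reversible". In the pooled adult Phase 3 trials, ALT rises above 3, 5 and 10 times ULN "were seen in 7.2%, 2.4% and 0.1% of solithromycin recipients". The rates above 3 times ULN "were 5.4% in the oral study and 9.1% in the IV to oral study".

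SAP Section 10.3.2 summarises the most extreme liver values and the largest increases from baseline. The output list in SAP Section 12 gives liver tables by treatment arm (14.4.3.2.4) and, within solithromycin, by consolidated age group and route (14.4.3.2.5). Nothing in the supplied text sets ALT against AUC or Cmax. SAP Section 2 sends the PK analyses to a PK data analysis plan in an appendix, which is not in the supplied text.

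**The concern.** The outcome chosen for the exposure question is poorly matched to the liver effect that makes the question important. A child whose ALT rises several-fold without symptoms, and who finishes the course, would normally enter this analysis as having had no event.

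Safety is the primary objective, and Section 5.4 says paediatric doses were chosen to match adult exposure. Whether liver enzymes rise with AUC or Cmax in children is therefore one of the more useful things the trial can show. A flat relation between exposure and AE proportion could be taken as reassurance while ALT rises with exposure.

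The split by route is a weak substitute. For IV dosing at 12 to 17 years, Section 5.4 gives a simulated Day 5 AUC0-24 with median 14.4 and standard deviation 23.4 mcg*h/mL, so exposure varies widely within one route.

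**Working it through.** **The plan's own figure.** The exposure-safety analysis states no sample size, power or threshold. The only related figure is Protocol Table 11, the chance of seeing at least one SAE at 1% incidence with 300 subjects: 1 - (1 - 0.01)^300 = 0.951, against 0.95 printed. It reproduces, but it concerns SAEs and says nothing about ALT.

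**Which ALT rises would be counted.** Under Section 12.1 a rise becomes an AE in three ways.

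1. Signs or symptoms: typically absent, according to Section 5.2.4.1.
2. Medical intervention: Section 5.2.4.1 describes the rises as readily reversible, many of them improving while dosing continued.
3. Interruption or discontinuation: this needs a result during dosing. Solithromycin is given for 5 to 7 days. The scheduled post-baseline samples (Sections 10.2 and 10.3) are at 72 hours (±24) on a best-effort basis, on the last dosing day or within 48 hours after it, and at Days 16 and 28. Only the first, plus any standard-of-care sample, can ordinarily come early enough to interrupt dosing.

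So some symptom-free rises are counted, probably a minority. The documents do not give the share.

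**Expected number with ALT above 3 times ULN** (N × adult rate, assuming adult rates apply to children). Enrolment was below one quarter of 400, so below 100. At 3:1 that is at most about 75 on solithromycin.

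| Source of rate | Rate | N = 300 | N = 75 |
|---|---|---|---|
| Adult oral study | 5.4% | 16.2 | 4.05 |
| Pooled adult Phase 3 | 7.2% | 21.6 | 5.4 |
| Adult IV-to-oral study | 9.1% | 27.3 | 6.8 |

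Above 5 times ULN (pooled 2.4%): 300 × 0.024 = 7.2 and 75 × 0.024 = 1.8.

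**What the choice of outcome does to the signal.** This is an illustration, since the plan has no test. Assume an overall ALT rate of 7.2% and three times the risk in the upper exposure half: lower half 2 × 7.2% / (1 + 3) = 3.6%, upper half 10.8%. Compare the halves with a two-sided 0.05 test of two proportions, counting rejection in the expected direction only (2.5% if there is no relation).

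- ALT above 3 times ULN counted directly, 150 per half: power 0.68.
- Any AE as the outcome, assuming 5% to 25% of ALT rises are coded as AEs and a 20% to 50% background AE rate: power about 0.03 to 0.05, close to the no-relation value. For example, with 25% coded and 20% background, the AE proportions are 1 - 0.8 × (1 - 0.25 × 0.036) = 0.207 and 1 - 0.8 × (1 - 0.25 × 0.108) = 0.222.
- Any AE, with every ALT rise coded as an AE: 0.09 to 0.21. The unrelated AEs alone dilute the signal.
- ALT counted directly, 37 per half (the terminated size): 0.22.

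The risk ratio, coded share and background rate are assumptions, not figures from the documents.

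**The case against.** Several points on the other side are sound.

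- **Some symptom-free rises are AEs.** A reader might infer that the analysis cannot detect an ALT effect at all. The interruption and discontinuation exception rules that out. Section 5.2.4.1 also reports that a transaminase increase below 3 times ULN was recorded as a related AE in the adolescent study CE01-119. That study's AE definition is not given, so this does not settle the matter.
- **ALT is not the only effect described as exposure-related.** Section 5.2.2.2.2 says the same of increased heart rate, in healthy adults at supratherapeutic IV exposure. Section 5.2.4.1 also reports fewer treatment-related gastrointestinal AEs at 1000 mg than at 1200 mg, which an AE count does capture. The AE and SAE proportions should stay.
- **The higher adult rates come partly from a different regimen.** In the IV-to-oral study CE01-301, patients who switched took a first oral dose of 800 mg (Section 5.2.3). This protocol uses no loading dose at the switch, and the Amendment 2 rationale says that load increased the potential for ALT elevations. The 9.1%, and part of the 7.2%, may therefore overstate what to expect here; hence the range from 5.4%.
- **Liver safety is watched elsewhere.** Section 12.1.3 sets weekly, quarterly and twice-yearly review of liver tests, and the SAP tabulates extremes. It would be wrong to infer that the trial neglects the liver. The gap is confined to one descriptive, secondary analysis.
- **The PK plan appendix cannot be seen.** It may already relate ALT to exposure. The SAP output list contains no PK output of any kind, so the absence of an ALT-by-exposure table there tells us nothing about the appendix.

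**Conclusion.** The concern holds in a limited form. On the supplied text, the only stated exposure-safety outcome is the proportion with AEs and SAEs. The AE definition probably leaves out most of the asymptomatic ALT rises for which the protocol reports an exposure-response relationship, and ALT is not set against exposure anywhere else.

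The number of children concerned is about 16 to 27 of 300 as planned, or at most about 4 to 7 of 75 after termination, if adult rates carry over. How many of them would be recorded as AEs is not documented, so saying most would be missed is a judgement from the AE definition, the typical absence of symptoms and the timing of the samples.

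Confidence is moderate, because the unseen PK plan may already close the gap. At the terminated size no version of the analysis can be more than descriptive. The PK population may be smaller still, since Section 10.4.3 does not treat missed PK samples as deviations.

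**What to change.** In Protocol Section 14.1.4, the synopsis and the PK analysis plan, keep the AE and SAE proportions and add a descriptive analysis in the PK population. It should show peak post-baseline ALT and AST as multiples of ULN, kept continuous and shown with or adjusted for baseline, against each subject's model-predicted AUC0-24 and Cmax. Subjects above 3 and 5 times ULN should be counted and listed by exposure. Proportions by exposure quartile are not worth planning at the terminated size: 5.4 / 4 is about 1.4 expected subjects above 3 times ULN per quartile at the pooled adult rate.

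Because the trial has ended, the PK plan is the practical place for the change. If the appendix already contains this analysis, say so and bring the protocol wording into line.

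The cost is a few sentences and one more table or plot. The liver tests and PK samples are already in the schedule, so no further subjects or blood draws are needed. The result should be labelled descriptive.
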